5.3.1 Occurrence of Adverse Events by Seriousness, Time of Onset, and Outcome

(1) Patients included in tabulation/analysis

Patients included in safety evaluation

(2) Data tabulated/analyzed

AEs will be categorized for each variable as described below, and the type of AE will be tabulated.

Variable	Category
Seriousness	Serious, non-serious
Time of onset	Days 1 to 180, Days 181 to 360, Day 361 or later
Outcome	Recovered, recovering, not recovered, recovered with sequelae, fatal, unknown

The type of AE will be tabulated as described below.

Variable	Data tabulated/analyzed
Number of patients	Number of patients who experienced an AE by SOC/PT
Number of AE	Number of reported AE by SOC/PT
Type of AE	
AEs will be classified by SOC and then tabulated by PT. For laboratory tests, AEs will be classified by SOC, then sorted by HLGT, and finally tabulated by PT.
 
AEs will be listed for SOC by SOC internationally agreed order and for PT in ascending order of PT code.
 
Multiple episodes of the same AE (PT) in the same patient will be tabulated by category as the total number of episodes (for instance, one episode of serious diarrhoea and one episode of non-serious diarrhoea in the same patient will be counted once in the respective categories).

(3) Table/figure number

Table 5.3-1

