9.2.5 Adverse Events (AEs)

1) Survey items

Presence or absence of AE (refer to Table 1), AE term, date of onset, seriousness and reason for seriousness (refer to Table 2), presence or absence of discontinuation of treatment with Zacras Combination Tablets, date of outcome assessment, outcome, causal relationship to Zacras Combination Tablets * (refer to Table 3)

Patients with "not resolved" or "unknown" outcome or "unevaluable" causal relationship should be followed up wherever possible.

* For the causal relationship to Zacras Combination Tablets, the rationale for "not related" and the reason for "unevaluable" shall be collected.

Note) Additional points to consider for AEs

Abnormal worsening of target disease, for instance, worsening beyond the expected natural course of the disease, will be handled as an AE, but expected worsening of target disease should not be handled as an AE.

2) Time points of survey

Period from the start of treatment with Zacras Combination Tablets to 12 months of

treatment (or discontinuation of treatment)

Table 1 Definition of adverse events

An AE is defined as any untoward medical occurrence in a clinical investigation subject administered a drug; it does not necessarily have to have a causal relationship with this treatment.
An AE can therefore be any unfavorable or unintended sign (e.g., abnormal laboratory finding), symptom, or disease temporally associated with the use of a drug, whether or not it is considered related to the drug.
The following are also handled as AEs:
•Symptoms and so forth that occur in infants breast-fed by their mothers under treatment with a drug
•Symptoms and so forth that occur in children treated with a drug
•Symptoms and so forth that occur as a result of occupational exposure to a drug
•Symptoms and so forth that occur after administration of counterfeit medicines of our ethical drugs

Table 2 Criteria for assessing seriousness

An AE satisfying any of the following is assessed as serious:
1. Results in death (death)
2. Is life-threatening (risk of death)
3. Requires inpatient hospitalization or prolongation of existing hospitalization (hospitalization/prolonged hospitalization)
4. Results in persistent or significant disability/incapacity (disability)
5. Leads to a congenital anomaly/birth defect (congenital anomaly)
6. Is an important medical event according to 1 to 5 described above, including AEs in Takeda Medically Significant AE List

Takeda Medically Significant AE List

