10.4.1 Occurrence of Adverse Events

For AEs reported during the observation period, the incidence will be tabulated by type, time of onset, seriousness, and causal relationship to Zacras Combination Tablets.

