5.0 Tabulation/Analysis of Safety

5.1 Occurrence of Adverse Events and Adverse Drug Reactions/Infections

5.1.1 Occurrence of Adverse Events

(1) Patients included in tabulation/analysis

Patients included in safety evaluation

(2) Data tabulated/analyzed

The following variables will be tabulated:

Variable	Data tabulated/analyzed
Number of patients with an AE	Number of patients who experienced an AE
Number of AE	Number of reported AE. Multiple episodes of the same AE (PT) in the same patient will be tabulated as the total number of episodes.
Incidence of AE	The incidence of AE will be calculated as number of patients with an AE/number of patients included in safety evaluation × 100.
Type of AE	AEs will be classified by SOC and then tabulated by PT. For laboratory tests, AEs will be classified by SOC, then sorted by HLGT, and finally tabulated by PT. For SOC, the number of patients with an AE and the incidence of AE will be listed by SOC internationally agreed order. For PT, the number of patients with an AE and the incidence of AE will be listed in ascending order of PT code. Multiple episodes of the same AE (PT) in the same patient will be tabulated as 1 patient.

(3) Table/figure number

Table 5.1-1

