5.1.2 Occurrence of Adverse Drug Reactions/Infections

(1) Patients included in tabulation/analysis

Patients included in safety evaluation

(2) Data tabulated/analyzed

The following variables will be tabulated:

Variable	Data tabulated/analyzed
Number of patients with an ADR, etc.	Number of patients who experienced an ADR, etc.
Number of ADR, etc.	Number of reported ADR, etc. Multiple episodes of the same ADR, etc. (PT) in the same patient will be tabulated as the total number of episodes.
Incidence of ADR, etc.	The incidence of ADR, etc. will be calculated as number of patients

	with an ADR, etc./number of patients included in safety evaluation $\times 100$.
Type of ADR, etc.	
ADRs, etc. will be classified by SOC and then tabulated by PT. For laboratory tests, ADRs, etc. will be classified by SOC, then sorted by HLGT, and finally tabulated by PT.
 
For SOC, the number of patients with an ADR, etc. and the incidence of ADR, etc. will be listed by SOC internationally agreed order.
 
For PT, the number of patients with ADR, etc. and the incidence of ADR, etc. will be listed in ascending order of PT code. Multiple episodes of the same ADR, etc. (PT) in the same patient will be tabulated as 1 patient.

(3) Table/figure number

Table 5.1-2

5.2 Occurrence of Adverse Events and Adverse Drug Reactions/Infections in Patients Excluded from Safety Evaluation

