5.3.2 Occurrence of Adverse Drug Reactions/Infections by Seriousness, Time of Onset, and Outcome

(1) Patients included in tabulation/analysis

Patients included in safety evaluation

(2) Data tabulated/analyzed

ADRs, etc. will be categorized for each variable as described below, and the type of ADR will be tabulated.

Variable	Category
Seriousness	Serious, non-serious
Time of onset	Days 1 to 180, Days 181 to 360, Day 361 or later
Outcome	Recovered, recovering, not recovered, recovered with sequelae, fatal, unknown

The type of ADR, etc. will be tabulated as described below.

Variable	Data tabulated/analyzed
Number of patients	Number of patients who experienced an ADR, etc. by SOC/PT
Number of ADR, etc.	Number of reported ADR, etc. by SOC/PT
Type of ADR, etc.	ADRs, etc. will be classified by SOC and then tabulated by PT. For laboratory tests, ADRs, etc. will be classified by SOC, then sorted by HLGT, and finally tabulated by PT. ADRs, etc. will be listed for SOC by SOC internationally agreed order and for PT in ascending order of PT code. Multiple episodes of the same ADR, etc. (PT) in the same patient will be tabulated by category as the total number of episodes (for instance, one episode of serious diarrhoea and one episode of non-serious diarrhoea in the same patient will be counted once in the respective categories).

(3) Table/figure number

Table 5.3-2

5.4 Incidence of Adverse Drug Reaction/Infection by Factors Related to Patient Demographics and Baseline Characteristics and Treatment Given

(1) Patients included in tabulation/analysis

Patients included in safety evaluation

(2) Data tabulated/analyzed

ADRs, etc. will be categorized for each variable as described below, and the incidence of ADR, etc. will be tabulated.

ADRs, etc. will be categorized for each variable as described below, and the type of ADR, etc. will be tabulated. The type of ADR, etc. will be tabulated as described in Section 5.1. For disposition of treatment with antihypertensive other than Zacras (at the start of treatment with Zacras) and disposition of treatment with antihypertensive other than Zacras (during the survey period), “other” will not be tabulated.

Variable	Category
Sex	Male, female
Age	<65 years, ≥65 years ----- <65 years, 65 to <75 years, ≥75 years
Predisposition to hypersensitivity	No, yes, unknown
Concurrent illness	No, yes

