5.5.1 Occurrence of Serious Adverse Events

(1) Patients included in tabulation/analysis

Patients included in safety evaluation

(2) Data tabulated/analyzed

The following variables will be tabulated:

Variable	Data tabulated/analyzed
Number of patients with a SAE	Number of patients who experienced a SAE
Number of SAE	Number of reported SAE Multiple episodes of the same SAE (PT) in the same patient will be tabulated as the total number of episodes.
Incidence of SAE	The incidence of SAE will be calculated as number of patients with a SAE/number of patients included in safety evaluation × 100.
Type of SAE	SAEs will be classified by SOC and then tabulated by PT. For laboratory tests, SAEs will be classified by SOC, then sorted by HLT, and finally tabulated by PT. For SOC, the number of patients with a SAE and the incidence of SAE will be listed by SOC internationally agreed order. For PT, the number of patients with a SAE and the incidence of SAE will be listed in ascending order of PT code. Multiple episodes of the same SAE (PT) in the same patient will be tabulated as 1 patient. The number of patients with a SAE not related to Zacro will be presented in parentheses.

(3) Table/figure number

Table 5.5-1

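### SAP 5.3 gives AE and ADR counts by onset window, not the incidence that Protocol 10.4.1 announces, and late counts fall with discontinuation even at constant risk

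*SAP*

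**What the plan says.** Protocol 10.4.1 states that for AEs in the observation period "the incidence will be tabulated by type, time of onset, seriousness, and causal relationship to Zacras Combination Tablets".

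The current SAP defines an incidence for three of these four factors:

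- Type, SAP 5.1.1: "The incidence of AE will be calculated as number of patients with an AE/number of patients included in safety evaluation".
- Causal relationship, SAP 5.1.2: the same form for adverse drug reactions, again over the safety set.
- Seriousness, SAP 5.5.1: "The incidence of SAE will be calculated as number of patients with a SAE/number of patients included in safety evaluation".

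For time of onset, SAP 5.3.1 and 5.3.2 set the windows "Days 1 to 180, Days 181 to 360, Day 361 or later". They then list a patient count ("Number of patients who experienced an AE by SOC/PT" and "Number of patients who experienced an ADR, etc. by SOC/PT") and an event count. Neither section has an incidence row, a denominator or an any-event total. No other section fills the gap: SAP 5.4 has no row for onset or treatment duration, and SAP 5.7 follows only pulse rate and laboratory values over time.

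Protocol 9.2.5 ends AE collection at 12 months of "treatment (or discontinuation of treatment"). SAP 4.0 tabulates treatment duration in the same safety population with the same cut points (Table 4.0-1). SAP 1.1 counts time of onset from the start of treatment and sets no upper limit. It also gives patients still on treatment at 12 months, with no recorded end date, an end date of start plus 360 days.

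**The concern.** There are two separate issues. The first is textual: the protocol announces an incidence by time of onset, and no table in the SAP delivers one.

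The second is about method. If collection stops when treatment stops, the number of patients who can contribute an event shrinks over the year. A lower count in Days 181 to 360 then mixes the risk with the number still observed. Dividing both windows by the whole safety set would satisfy the protocol's wording but leave the late-to-early ratio unchanged.

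The survey's objective is the safety of long-term use, and these two tables are the only place where a reader sees when events occur. Read alone, they lean towards a reassuring picture of falling late risk.

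**Working it through.** The plan states no figure to reproduce here. Protocol 3.2 says that the 1,000 patients do not come from a statistical calculation, and neither document gives a discontinuation rate. The rates below are assumptions.

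**1. Counts at constant risk.** Let *d* be the share stopping by Day 360, spread evenly over the year. The mean share observed is 1 − 0.25*d* in Days 1–180 and 1 − 0.75*d* in Days 181–360. The late-to-early count ratio is (1 − 0.75*d*)/(1 − 0.25*d*). The share on treatment at Day 181 is 1 − 0.5*d*, so the ratio of incidences per patient entering the window is [(1 − 0.75*d*)/(1 − 0.5*d*)]/(1 − 0.25*d*).

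| *d* | Early observed | Late observed | Count ratio | On treatment at Day 181, per 1,000 | Incidence ratio |
|---|---|---|---|---|---|
| 10% | 0.975 | 0.925 | 0.949 | 950 | 0.999 |
| 25% | 0.9375 | 0.8125 | 0.867 | 875 | 0.990 |
| 40% | 0.900 | 0.700 | 0.778 | 800 | 0.972 |

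The true ratio is 1 throughout. The pattern of stopping matters little. With a constant hazard of stopping, counts fall by 5.1% at 10% and 22.5% at 40%. With two-thirds of stopping in the first half-year, they fall by 5.2% and 23.1%.

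**2. Whole-set percentages do not help.** Take 1,000 patients, an assumed 0.10 events per 180 patient-days, and 20% stopping at a constant hazard. The expected counts are 94.6 early and 84.6 late. As percentages of the safety set these are 9.46% and 8.46%. On the 894 patients entering the second window, the late figure is 84.6/894 = 9.46%.

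**3. The numerator must match.** Suppose a share *c* of time after stopping still yields recorded events. The early and late observed shares become 1 − 0.25*d*(1 − *c*) and 1 − 0.75*d*(1 − *c*). At *d* = 25%:

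| *c* | Count ratio | Incidence ratio, numerator unrestricted |
|---|---|---|
| 0 | 0.8125/0.9375 = 0.87 | 0.99 |
| 0.5 | 0.90625/0.96875 = 0.94 | (0.90625/0.875)/0.96875 = 1.07 |
| 1 | 1.00 | 1/0.875 = 1.14 |

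An on-treatment denominator with unrestricted events can therefore overshoot. Counting only events with onset up to the end of treatment brings every row back to *c* = 0.

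**4. Stopping related to events.** With 25% discontinuing and a base rate of 0.1 events per year, let 20% of patients have 4 times that rate and 30% of events lead to stopping. Counts then give 0.86 and the corrected incidence 0.99. With 10% of patients at 8 times the rate and 50% of events leading to stopping, the figures are 0.82 and about 0.95.

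**5. Last window.** With an end date of start plus 360 days, which is Day 361, this window holds about one day of observation. At the rate in step 2, and 0% to 40% constant-hazard discontinuation, that is 0.3 to 0.6 expected events against 88 to 100 in the first window. An incidence there would mean little.

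**6. Chance.** For 50 early and 43 late events (ratio 0.86), the standard error of the log ratio is √(1/50 + 1/43) = 0.208. The 95% interval is about 0.57 to 1.29.

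**The case against.** *The premise is not airtight.* Protocol 7.1 sets a 12-month observation period without qualification, and 7.5 and 10.4.1 refer to events in that period. A reader might infer from 9.2.5 that no event after stopping can ever enter the tables. The documents do not support that, because the SAP has no cut-off removing later-onset AEs. Protocol 9.2.5 is nevertheless the specific rule for AE collection. Protocol 7.4 speaks of an end of required observation for patients who stop, and its follow-up after stopping for an AE concerns the outcome of that event. The main reading stands, and the objection correctly forces the numerator rule.

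*The protocol promises incidence, not at-risk incidence.* This stands. A reader might infer that the SAP breaks a commitment to an on-treatment denominator. There is no such commitment, and every incidence in the current SAP uses a fixed analysis set. The departure from the protocol is only the absent incidence; the at-risk denominator is an improvement in method.

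*Table 4.0-1 already holds the information.* Largely true: adding its two upper duration categories gives the number on treatment at Day 181. But SAP 5.3 does not refer to that table.

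*The effect is hypothetical and may be small.* This also stands. At 5% discontinuation the count ratio is 0.9625/0.9875 = 0.97. At 25% the effect lies within chance for about 50 early events, and at preferred-term level chance will usually dominate.

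**Conclusion.** The point holds as a reporting gap that should be closed. The mismatch between Protocol 10.4.1 and SAP 5.3 needs no assumption. The distortion from counts rests on collection ending at discontinuation, on constant risk and on an assumed discontinuation rate: late-to-early ratios of about 0.95, 0.87 and 0.78 at 10%, 25% and 40%. It matters most for totals and larger organ classes.

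A reader might go further and infer that the survey will understate long-term risk. The documents do not support that. The counts themselves are correct, no test across windows is planned, overall and serious-event incidence are specified elsewhere, and no discontinuation rate is given.

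SAP 1.1 also sets incomplete onset dates to the earliest compatible date, which can only move events earlier. The share of such dates is unknown, and the conclusion does not rest on it.

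**What to change.** In Tables 5.3-1 and 5.3-2, for Days 1–180 and Days 181–360:

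- Add the number on treatment at the start of the window (duration of at least 1 and at least 181 days, as derived for Table 4.0-1), the incidence on that number, and an any-event total row.
- For this incidence, count only events with onset on or before the end date of treatment. Show recorded later-onset events separately as counts.
- State how many patients have no derivable duration. SAP 2.0 keeps patients without a follow-up CRF in the safety set, so some may exist.
- Report counts only for the open last window.
- Add a note that discontinuation related to events is not fully corrected.

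A sensitivity table for incomplete onset dates is optional. The cost is SAP wording, a few columns and rows in two descriptive tables, and one numerator rule. The durations are already derived, and no new data are needed.

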5.3.2 Occurrence of Adverse Drug Reactions/Infections by Seriousness, Time of Onset, and Outcome

(1) Patients included in tabulation/analysis

Patients included in safety evaluation

(2) Data tabulated/analyzed

ADRs, etc. will be categorized for each variable as described below, and the type of ADR will be tabulated.

Variable	Category
Seriousness	Serious, non-serious
Time of onset	Days 1 to 180, Days 181 to 360, Day 361 or later
Outcome	Recovered, recovering, not recovered, recovered with sequelae, fatal, unknown

The type of ADR, etc. will be tabulated as described below.

Variable	Data tabulated/analyzed
Number of patients	Number of patients who experienced an ADR, etc. by SOC/PT
Number of ADR, etc.	Number of reported ADR, etc. by SOC/PT
Type of ADR, etc.	ADRs, etc. will be classified by SOC and then tabulated by PT. For laboratory tests, ADRs, etc. will be classified by SOC, then sorted by HLGT, and finally tabulated by PT. ADRs, etc. will be listed for SOC by SOC internationally agreed order and for PT in ascending order of PT code. Multiple episodes of the same ADR, etc. (PT) in the same patient will be tabulated by category as the total number of episodes (for instance, one episode of serious diarrhoea and one episode of non-serious diarrhoea in the same patient will be counted once in the respective categories).

(3) Table/figure number

Table 5.3-2

5.4 Incidence of Adverse Drug Reaction/Infection by Factors Related to Patient Demographics and Baseline Characteristics and Treatment Given

(1) Patients included in tabulation/analysis

Patients included in safety evaluation

(2) Data tabulated/analyzed

ADRs, etc. will be categorized for each variable as described below, and the incidence of ADR, etc. will be tabulated.

ADRs, etc. will be categorized for each variable as described below, and the type of ADR, etc. will be tabulated. The type of ADR, etc. will be tabulated as described in Section 5.1. For disposition of treatment with antihypertensive other than Zacras (at the start of treatment with Zacras) and disposition of treatment with antihypertensive other than Zacras (during the survey period), “other” will not be tabulated.

Variable	Category
Sex	Male, female
Age	<65 years, ≥65 years ----- <65 years, 65 to <75 years, ≥75 years
Predisposition to hypersensitivity	No, yes, unknown
Concurrent illness	No, yes

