3.2 Rationale

Patient populations identified as important missing information from Japanese clinical studies of Zacras Combination Tablets are patients with renal impairment, patients with hepatic impairment, and elderly patients (≥ 75 years old). The sample size required to evaluate the safety and efficacy of long-term use of Zacras Combination Tablets in these patient populations was calculated by reference to previous results. More specifically, according to final tabulation (number of patients included in safety evaluation: 3,300) in a previous specified drug-use survey (long-term use survey in hypertension) of a fixed-dose combination (UNISIA Combination Tablets) of an angiotensin receptor blocker (ARB) (candesartan) and a Ca antagonist (amlodipine), which belongs to the pharmacologically same class as Zacras Combination Tablets, patients with renal impairment, patients with hepatic impairment, and elderly patients (and those ≥ 75 years old) accounted for 6.9%, 11.5%, and 65.2% (36.8%) of all patients, respectively. According to final tabulation (number of patients included in safety evaluation: 4,152) in a drug use-results survey of candesartan alone (BLOPRESS Tablets), patients with renal impairment, patients with hepatic impairment, and elderly patients (and those ≥ 75 years old) accounted for 9.5%, 10.6%, and 53.2% (22.1%), respectively. With a target sample size of 1,000 patients for the present survey, 70 patients with renal impairment, 100 patients with hepatic impairment, and 500 elderly patients (and 200 patients ≥ 75 years old)

are expected to be collected, probably allowing the safety and efficacy evaluation in these populations. This calculation is not based on statistical estimation.

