•Acute respiratory failure/acute respiratory distress syndrome (ARDS)	•Anaphylactic shock
•Torsade de pointes / ventricular fibrillation / ventricular tachycardia	•Acute renal failure
•Malignant hypertension	•Pulmonary hypertension
•Convulsive seizures (including convulsion and epilepsy)	•Pulmonary fibrosis (including interstitial pneumonia)
•Agranulocytosis	•Neuroleptic malignant syndrome / malignant hyperthermia
•Aplastic anemia	•Spontaneous abortion / stillbirth and fetal death
•Toxic epidermal necrolysis / oculomucocutaneous syndrome (Stevens-Johnson syndrome)	•Confirmed or suspected transmission of infectious agent by a medicinal product
•Hepatic necrosis	•Confirmed or suspected endotoxin shock
•Acute liver failure	

Table 3 Criteria for assessing the relationship of each adverse event to Zacras Combination**Tablets**

Assessment	Criteria for assessment
Related	An AE that follows a reasonable temporal sequence from administration of a drug (including the course after withdrawal of the drug), or for which possible involvement of the drug can be argued, although factors other than the drug, such as underlying diseases, concurrent illnesses, concomitant drugs, and concomitant treatments, may also be responsible
Not related	An AE that does not follow a reasonable temporal sequence from administration of a drug and/or that can reasonably be explained by other factors, such as underlying diseases, concurrent illnesses, concomitant drugs, and concomitant treatments
Unevaluable	Information necessary for evaluation, including temporal sequence from administration of a drug (including the course after withdrawal of the drug), underlying diseases, concurrent illnesses, concomitant drugs, and concomitant treatments, is not sufficient.

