10.4.2 Factors that May Affect the Safety

For AEs reported during the observation period, the incidence will be tabulated by patient background factors (e.g., sex, age, presence or absence of concurrent renal impairment, presence or absence of concurrent hepatic impairment) and treatment given (e.g., details on the use of Zacras Combination Tablets, details on the use of concomitant drug).

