14.0 Other Necessary Matters

14.1 Revision of the Protocol

[figure not shown]
[figure not shown]
[figure not shown]
[figure not shown]
[figure not shown]
[figure not shown]
[figure not shown]
[figure not shown]
[figure not shown]
During the survey, attention will be paid to comprehend the status of progression of the survey, presence or absence of unexpected adverse drug reactions (ADRs)/serious ADRs (based on precautions), presence or absence of increased incidence of certain ADRs, and appropriateness of survey items, and this protocol will be reviewed and revised if necessary. If partial change to dosage and administration or indications is approved during the survey, the necessity of revising the protocol will be discussed if necessary, and the protocol will be revised as needed.

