Duration of disease	(Start date of treatment with Zacras - time of diagnosis of hypertension + 1) $\div 365.25$. For time of diagnosis of hypertension, 1 will be used as the day, and January 1 will be used if the month is unknown. The duration of disease will be handled as missing if the year, month, and day are unknown.
ADR, etc.	Abbreviation of “adverse drug reaction/infection” AE other than those assessed by the investigator to be not related to Zacras In this document, “adverse drug reaction/infection” is used in titles, and “adverse drug reaction, etc.” is used in the text and tables.
SAE	Adverse event assessed by the investigator to be serious Events included in the MedDRA code list in Takeda Medically Significant AE List will be handled as serious even if assessed by the investigator to be non-serious.
Number of patients with an AE or an ADR, etc.	Number of patients who experienced an AE or an ADR, etc.
Number of AE or ADR, etc.	Number of reported AE or ADR, etc.
Time of onset	Time of onset will be calculated as date of onset of AE (or ADR, etc.) - start date of treatment + 1. If the month and day of AE (or ADR, etc.) are unknown, January 1 will be used for calculation. If an AE (or ADR, etc.) occurs in the same year as treatment is started, the month and day of starting treatment will be used for calculation. If the day of AE (or ADR, etc.) is unknown, 1 will be used for calculation. If an AE (or ADR, etc.) occurs in the same year and month as treatment is started, the start date of treatment will be used for calculation. If the year, month, and day of AE (or ADR, etc.) is unknown, the start date of treatment will be used for calculation.
Patient with concurrent diabetes	Patient with a check for diabetes in the column of concurrent illness in the CRF or concurrent illness corresponding to Standardised MedDRA query (hereinafter referred to as SMQ) code 20000041 (hyperglycaemia/new onset diabetes mellitus SMQ [scope: narrow]) described
Patient with concurrent dyslipidemia	Patient with a check for dyslipidemia in the column of concurrent illness in the CRF or concurrent illness corresponding to SMQ code 20000026 (dyslipidaemia SMQ [scope: narrow]) described
Patient with concurrent hyperuricemia	Patient with a check for hyperuricemia in the column of concurrent illness in the CRF or concurrent illness corresponding to MedDRA PT code 10020903 (hyperuricaemia) described

Term	Definition

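### The SAP's by-factor safety tables leave out adverse events judged not related, although Protocol 10.4.2 calls for all adverse events by factor

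*SAP*

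**What the plan says.** - **Protocol 10.4.2** sets the requirement: "For AEs reported during the observation period, the incidence will be tabulated by patient background factors". Its examples are sex, age, concurrent renal impairment and concurrent hepatic impairment. It asks for the same by treatment given (use of Zacras, concomitant drugs).
- **Protocol 10.4.1** covers the same events without patient factors: "the incidence will be tabulated by type, time of onset, seriousness, and causal relationship to Zacras Combination Tablets".
- **SAP 5.4** is where the by-factor safety analysis is planned: "ADRs, etc. will be categorized for each variable as described below, and the incidence of ADR, etc. will be tabulated". A second sentence plans the type of ADR by the same variables, tabulated as in Section 5.1. The tables are numbered 5.4.2-1 to -26.
- **SAP 1.1** defines ADR, etc. as any "AE other than those assessed by the investigator to be not related to Zacras". Events rated unevaluable stay in; events rated not related drop out.
- **Protocol 3.2** explains why the sample is 1,000. "Patient populations identified as important missing information from Japanese clinical studies" are those with renal impairment, those with hepatic impairment, and those aged 75 or over. Expected numbers are 70, 100 and 200.

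**The concern.** The protocol's unit for this analysis is the AE; the SAP's unit is the ADR. An analyst who follows the SAP exactly will not produce a result that the protocol promises.

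The missing part matters most for the three priority groups. With ADRs alone, every subgroup safety figure has already passed through the investigator's causality judgement. Table 3 in Protocol 9.2.5 allows a not-related rating when the event "can reasonably be explained by other factors, such as underlying diseases, concurrent illnesses" and the like, and concurrent illness is what defines two of the three groups. If investigators more readily attribute events to the existing kidney or liver disease, ADR incidence in those groups would look lower than it should. Nothing in the by-factor output would show it.

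**Working it through.** **1. Does AE in 10.4.2 perhaps mean ADR?** No. Section 10.4.1 opens in the same way and treats causal relationship as one breakdown of AEs, so AEs there include events of every causality rating. Where the protocol means ADRs it says so: Section 14.1 asks the sponsor to watch for "presence or absence of increased incidence of certain ADRs". The SAP also keeps the two apart, with paired AE and ADR sections at 5.1.1/5.1.2 and 5.3.1/5.3.2.

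**2. Does any other SAP section supply AEs by factor?**

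| SAP section | Events | Split by patient or treatment factor? |
|---|---|---|
| 5.1.1 | AEs, all safety patients | No |
| 5.2.1, 5.6.1 | AEs and SAEs, patients excluded from safety evaluation | No |
| 5.3.1 | AEs by seriousness, onset, outcome | No |
| 5.4 | ADR, etc. only | Yes |
| 5.5.1 | SAEs, not-related count in parentheses | No |
| 5.7 | Pulse rate and laboratory values | No; not AEs |

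The remaining safety sections (5.1.2, 5.2.2, 5.3.2, 5.5.2, 5.6.2) cover ADRs and are not split by factor. SAP 6.4 does split by factor, but for blood pressure. AE-by-factor tables: 0.

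**3. Could the 26 numbered tables hide some AE tables?** Counting the 5.4 variable list:

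- sex 1 + age 1 + hypersensitivity 1 + concurrent illness 1 = 4
- named illnesses 9, running total 13
- initial dose 1 + dose change 1 + switching 1, running total 16
- other antihypertensive at start 1 + 4 drug classes, running total 21
- other antihypertensive during the survey 1 + 4 drug classes, running total 26

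The class *other* is not counted because 5.4 says it is not tabulated. This reproduces the plan's 26, taking the two age splits as one table (27 if counted separately). The ADR list alone fills the allotted numbers.

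**4. Denominator.** Section 5.4 states none and refers to Section 5.1 for the type tables. There the incidence denominator (5.1.2) is all patients included in safety evaluation. If that were carried over literally, and all 1,000 planned patients were evaluable, subgroup percentages would be too small by these factors: 1,000/70 = 14.3 (renal), 1,000/100 = 10 (hepatic) and 1,000/200 = 5 (aged 75 or over). The sensible reading is a subgroup denominator, but it is not written down.

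**5. What cannot be computed.** Neither document gives an AE rate or the share of AEs expected to be rated not related. The number of omitted events, and any bias, therefore cannot be estimated.

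**Which SAP text.** I take the SAP text placed first in the file as current. The 2nd edition, dated 16 October 2017, has the same 5.4, so the finding holds for either. The earliest edition planned AE incidence by factor (its 5.4.1). I use that only to show that such tables are feasible; the change between editions is not itself the defect.

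**The case against.** The best case for leaving the plan alone is that little is lost.

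- The ADR definition is wide: it keeps every event not positively judged not related, including unevaluable ones.
- Table 3 also lets an event count as related when concurrent illness may share responsibility.
- The reason for each not-related rating is collected (Protocol 9.2.5).
- All AEs still appear overall, and unrelated SAEs are shown separately.
- The survey has one arm and unadjusted tables, so AE incidence in older or renally impaired patients will partly reflect background illness. It would not by itself expose misjudged causality.

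These points stand as limits on the consequence, and they are why bias is described as possible rather than shown. They do not remove the mismatch. The protocol promised a specific result, and its usefulness does not depend on settling causality: shown beside ADR incidence, it lets a reader see how much of each subgroup's event burden was set aside.

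A second objection is that three added tables would still not satisfy 10.4.2, which also names sex and treatment given. That is correct. Three tables are a floor for the priority groups; full conformity needs the whole 5.4 list.

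A third is timing. Under Protocol 8.0 the survey period ended on 31 January 2017, before the 2nd SAP edition, so amending the protocol would come after the planned data collection. This favours correcting the SAP.

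**Conclusion.** The concern holds and should be fixed. The current SAP plans 26 by-factor safety tables for ADR, etc. and none for AEs, against an explicit protocol commitment to AEs. The omission affects the renal, hepatic and 75-and-over groups on which the sample size rests. No data are lost, because not-related AEs remain in the overall tables; what is missing is their breakdown by subgroup. The conclusion comes from reading the two documents side by side and needs no assumed rates. The group sizes of 70, 100 and 200 are the protocol's expectations, which it says are not based on statistical estimation.

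**What to change.** In SAP 5.4, keep the present factor list and add AE incidence next to ADR incidence:

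- Define it as patients in the subgroup with an AE, divided by patients in that subgroup, times 100, with both counts shown.
- Write out the same subgroup denominator for the ADR figures.
- Add no significance tests.
- Cover the full list. As a floor, cover age (including 75 and over), renal impairment and hepatic impairment, and state and justify the departure for the other factors in 10.4.2.

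If the sponsor prefers ADRs only, amend Protocol 10.4.2 and state the reason there and in the SAP.

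The cost is SAP wording and table programming. The floor is 3 extra tables. Separate AE tables for the full list would add 26, giving 26 + 26 = 52. AE and factor data are already collected, and no sample size or significance level changes.
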